1.0 PROTOCOL SUMMARY AND/OR SCHEMA

This is a single-center, open-label phase II study of the combination of tafasitamab and lenalidomide in relapsed or refractory (R/R) mantle cell lymphoma (MCL) who have received previous treatment with a Bruton's tyrosine kinase inhibitor (BTKi). The study aims to evaluate the efficacy of the combination therapy. The primary endpoint will be objective response rate (ORR) to tafasitamab and lenalidomide, and will be evaluated when all patients have completed 12 cycles of treatment or at treatment discontinuation, whichever comes first.

Patients will be enrolled to receive tafasitamab via IV infusion and self-administer lenalidomide orally according to the treatment schema below, for a maximum of 36 cycles (3 years). In the first stage of the Simon 2-stage design, a total of 19 patients will accrue. If 6 or fewer have objective response, the trial will close due to a lack of efficacy; otherwise, an additional 20 patients will accrue. If at the end of the study, 17 or more out of 39 have an objective response, the trial will be considered promising for future development.

[figure not shown]
The anticipated accrual rate for this study is 1 to 2 patients per month, and the trial will continue through three years after the last accrued patient.

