2.3 Exploratory objectives

- 2.3.1** To assess the rate of conversion to undetectable minimal residual disease (MRD) by immunoglobulin gene next-generation sequencing (NGS) relative to baseline at 3, 6, and 12 months post initiation of study treatment; MRD will also be assessed at POD.
- 2.3.2** To characterize clonal evolution using circulating tumor DNA (ctDNA) in peripheral blood via high-depth targeted genomic sequencing at baseline, at 3, 6, and 12 months post initiation of study treatment, and at POD.
- 2.3.3** To evaluate effects of study treatment on:
 - Antitumor immune response (via surface protein expression, RNA expression, and variable, diversity, and joining (V(D)J) gene segment recombination of peripheral mononuclear cells (PBMCs)) relative to baseline at 3, 6, and 12 months post initiation of study treatment, and at POD.
 - MCL-driven immunosuppression in the tumor microenvironment (via flow cytometry enumeration of lymphocyte subsets in tumor biopsy samples) relative to baseline between days 21-28 of cycle 1, and at POD.

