to determine whether progression of disease in patients occurs because a) activity of Ikaros family transcription factors is restored, or b) immune suppression persists in the absence of recurrent Ikaros-dependent transcriptional activation.

4. Minimal residual disease (MRD)

MRD assessment can further refine response assessment in MCL and provides prognostic information in MCL [33558202]. In this study, we will perform MRD assessment using a next generation immunosequencing (IS) MRD assay (Adaptive Biotechnologies, Seattle, WA). This IS MRD assay leverages multiplex PCR followed by NGS to identify and track rearrangements of IgH, V-J, D-J and IgK/L loci and translocations in Bcl1/2-IgH. Peripheral blood will be collected at screening, day 1 of cycles 3, 7, and 13, and at end of treatment for MRD analysis, and evaluated for association with progression-free survival.

5. Clonal evolution in MCL.

Dynamic molecular monitoring in MCL patients treated with biologically targeted agents, such as ibrutinib and venetoclax, have revealed mutations that mediate therapeutic resistance [30455436]. In this study, we aim to characterize the clonal evolution of MCL in serial patient samples on treatment with tafasitamab and lenalidomide. Patients will have ctDNA in peripheral blood collected and banked for genomic testing by high-depth targeted sequencing pretreatment and serially during therapy, in order to study the effect of protocol therapy on clonal composition of MCL and assess whether genetic alterations arise that are associated with resistance. An MSK platform for assessment of circulating tumor DNA in peripheral blood specimens will be utilized.

6. Tumor molecular profiling and prognosis

Molecular analysis of diagnostic tumor samples obtained during screening with paired normal tissue (saliva or nails) will be analyzed using the MSK IMPACT platform under IRB protocol 12-245. Genomic alterations in MCL will be analyzed for associations with key clinical outcomes including PFS, ORR, and OS.

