13.2 Criteria for Study Endpoint Evaluability

All patients who received at least one dose of tafasitamab and one dose of lenalidomide will be considered evaluable for the primary endpoint of ORR and all secondary endpoints. This will be the primary analysis. Safety endpoints will be evaluated in all patients who received at least one dose of tafasitamab or one dose of lenalidomide. Any patient that is removed from the study for reasons other than progression will be counted as a failure for ORR analysis and as an event for PFS analysis (as long as they have received at least 1 dose of tafasitamab and 1 dose of lenalidomide). For OS analysis, patients who are removed from the study for any reason other than death will be censored at the time of study removal. The study will continue enrollment until the required number of evaluable patients (those that receive at least one dose of both study drugs) is reached in each stage of the study.

The primary and secondary endpoints will also be evaluated in the per-protocol cohort (patients who did not have any major protocol violations) as a supportive, secondary analysis.

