Primary objectives: ORR will be calculated as a proportion and summarized along with 95% confidence intervals. Patients who withdraw prior to response evaluation will be classified as nonresponders for the primary objective.

Secondary objectives: OCR will be defined as the percent of patients who achieve CR, PR or stable disease (SD) at the time of ORR assessment. Patients who withdraw prior to response evaluation will be classified as failures. The OCR will be estimated by proportion along with 95% confidence intervals. DOR will be defined as the time from achievement of PR or CR to progression of disease (POD) according to Lugano criteria or death. PFS will be defined as the time from initiation of study treatment to the earlier of POD or death from any cause. OS will be defined as the time from initiation of treatment to death from any cause. Kaplan-Meier estimates of DOR, PFS, and OS will be calculated and presented with 95% confidence intervals. TTP will be defined as the time from start of treatment to POD or death specially from MCL, and will be estimated with 95% confidence intervals by cumulative incidence function. Death from other causes will be treated as a competing risk. Frequency and severity of adverse events will be summarized descriptively.

Exploratory objectives will be performed in conjunction with collaborating laboratories at MSK. Study designs and analytic approaches are detailed in Section 3.1. Most objectives will be summarized descriptively. For assessing association between minimal MRD and PFS, the log rank test will be used and Kaplan-Meier curves will be presented. For assessing association between genomic alterations discovered through MSK-IMPACT sequencing and time-to-event outcomes PFS and OS, Cox regression will be used and hazard ratios with 95% confidence intervals will be presented. For assessing association between genomic alterations and ORR, Fisher's exact test will be used, and p-values will be adjusted for multiple testing with the false discovery rate (FDR).

14.1 Populations for analysis include the following:

- Primary analysis (primary endpoint and all secondary endpoints): All patients who received at least one dose of tafasitamab and one dose of lenalidomide
- Safety analysis: All patients who received at least one dose of tafasitamab or one dose of lenalidomide

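### The exploratory MRD–PFS log-rank test names no draw, patient set or landmark, although conversion to undetectable MRD becomes known only after PFS has started (low priority)

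*Combined protocol and SAP*

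**What the plan says.** All references are to the combined protocol and SAP.

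- **Test.** Section 14.0, exploratory methods: "For assessing association between minimal MRD and PFS, the log rank test will be used and Kaplan-Meier curves will be presented". That paragraph refers to Section 3.1 for analytic detail.
- **Time origin.** Section 14.0: "PFS will be defined as the time from initiation of study treatment to the earlier of POD or death from any cause".
- **Draws.** Section 3.1, item 4: "Peripheral blood will be collected at screening, day 1 of cycles 3, 7, and 13, and at end of treatment for MRD analysis". The sentence ends "and evaluated for association with progression-free survival" and gives no method.
- **Objective.** Section 2.3.1 concerns conversion to undetectable MRD relative to baseline, "at 3, 6, and 12 months post initiation of study treatment; MRD will also be assessed at POD".
- **Early removals.** Section 13.2 says that patients taken off study "for reasons other than progression will be counted as a failure for ORR analysis and as an event for PFS analysis".
- **Populations.** Section 14.1 defines sets for the primary and secondary endpoints, for safety and for the per-protocol analysis. It defines none for MRD. Section 11.2 refers only to Table 11-1 and a lab manual.

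No landmark or time-dependent method appears anywhere in the plan.

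**The concern.** A log-rank test needs groups that are known when the clock starts. Here the clock starts at cycle 1 day 1, while the status of interest is established during treatment. Suppose patients who progress, die or leave before a draw are counted as not undetectable. Staying event-free then becomes a condition of entry to the undetectable group, and MRD clearance can look prognostic when it is not. The Section 13.2 rule adds to this under such a grouping: an early removal is an early PFS event in a patient who has no later visit draw.

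What is at stake is the credibility of one exploratory biomarker result. No decision rule, sample size or ORR conclusion depends on it.

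**Working it through.** The plan states no event count, power or significance level for this test, so there is no figure to reproduce.

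**1. When status becomes known.** Cycles last 28 days (Section 4.2), and 30.44 days are taken as one month.
- C3D1: 2 × 28 = 56 days; 56 / 30.44 = 1.8 months
- C7D1: 6 × 28 = 168 days; 168 / 30.44 = 5.5 months
- C13D1: 12 × 28 = 336 days; 336 / 30.44 = 11.0 months

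**2. Why all-patient groupings are biased.** Assume that each visit draw is undetectable with probability q, independently of PFS. A patient who reaches k visit draws is then ever undetectable with probability 1 − (1 − q)^k. For k = 0, 1, 2, 3 this gives 0, 0.20, 0.36, 0.488 at q = 0.2 and 0, 0.30, 0.51, 0.657 at q = 0.3. Group membership therefore rises with event-free time even though MRD has no relation to PFS.

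**3. Why the single-visit comparison is unbiased.** If only patients sampled and event-free at one draw are included, none has an event before it. The risk sets at every event time are then the same whether time runs from treatment start or from the draw, and so is the log-rank statistic. The Kaplan-Meier curves do differ: from treatment start they stay at 100% for 56, 168 or 336 days. With exponential PFS and an assumed cohort median of 6–12 months, curves for patients sampled at C7D1 would show medians of 5.5 + 6 = 11.5 to 5.5 + 12 = 17.5 months.

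**4. Illustrative size.** The sample of 39 comes from Section 14.0. The other inputs are assumptions: exponential PFS with median 6, 9 or 12 months, 20% or 30% undetectable per draw, cut-off at 36 months, and no MRD–PFS association. The simulation used 5,000 trials per scenario and a nominal 5% log-rank test.

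| Grouping | Rejection rate |
|---|---|
| Ever v never, three visit draws, independent | 25.0–62.2% |
| As above, plus end-of-treatment draw at the same clearance rate | 19.5–44.1% |
| As above, end-of-treatment draw undetectable only without progression | 37.8–65.3% |
| Ever v never, half keep their status between draws | 11.9–32.8% |
| Ever v never, status fixed by C3D1 | 5.0–8.1% |
| C7D1 undetectable v everyone else | 7.6–24.6% |
| C13D1 undetectable v everyone else | 14.4–37.1% |
| Event-free patients sampled at one visit | 5.3–9.0% |
| C7D1 sampled patients only, permutation p-value (1,000 trials, 199 permutations) | 4.1–5.6% |

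In the sampled-only row, only 1.3–2.7 percentage points favour undetectable MRD. The excess over 5% is small-sample error of the asymptotic test, not immortal-time bias.

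A separate run with wider assumptions (median 4–12 months, clearance 15–50%, 3,000 trials per scenario) gave 17–93% for ever versus never, 5–71% for C7D1 versus everyone else, and 5.6–9.3% for a landmark at a fixed draw.

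**5. Patients left at a C7D1 landmark.** The expected number is 39 × 2^(−5.52/median). This gives 20.6 at a median of 6 months, 25.5 at 9 and 28.4 at 12. At 20–30% clearance, about 4–9 of them are undetectable.

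**The case against.** The strongest reply is that this is silence, not error. No section proposes ever versus never, or a late draw versus everyone else. A competent analyst could compare sampled, event-free patients and obtain an unbiased test. That stands: a reader might infer that the planned analysis is biased as written, and the documents do not support that reading. But the plan commits to a named test, and its time origin makes several natural groupings biased. The unbiased one still yields misleading curves, so this is more than a request for detail.

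Second, MRD is also drawn at screening, before PFS starts. This too is right, and the point is confined to on-treatment status. Section 2.3.1 concerns conversion relative to baseline, which the screening draw cannot show.

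Third, the rejection rates rest on assumptions and are sensitive to how far status persists between draws. That stands in full. A reader might take 25–62% as this trial's false-positive rate, but the documents give neither input needed to say so.

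Fourth, the 100% plateau holds only if the compared patients are event-free at the draw. Section 12.0 says that progressing patients may be withdrawn, not that they must be. The plateau is therefore claimed only for the event-free comparison.

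**Conclusion.** The point holds as an inexpensive improvement to an exploratory analysis, at low priority. Three things follow without outside figures: on-treatment MRD status post-dates the PFS origin; all-patient groupings that the text permits favour undetectable MRD; and curves from treatment start for patients event-free at a draw contain 1.8, 5.5 or 11.0 months of guaranteed event-free time.

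The size of the bias is not derivable from the documents. Under the assumed ranges it runs from near nominal (status fixed by C3D1) to several times 5% (ever versus never with independent draws).

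**What to change.** Replace the Section 14.0 sentence with wording such as:

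> The MRD–PFS association will be described by a landmark analysis at one pre-specified draw (e.g. C7D1), in evaluable patients with an MRD result at that draw and no PFS event by then. Groups are undetectable versus detectable MRD at that draw. PFS is counted from that draw, with Kaplan-Meier curves and a log-rank test using a permutation p-value because groups are small. Other visit draws are supportive and descriptive. The end-of-treatment or POD sample does not define groups.

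C7D1 is only an example; any single draw fixed before the analysis will serve. Use the same PFS event definition as the main PFS analysis, and state it: Section 13.2 counts removal for reasons other than progression as an event, while Sections 2.2.3 and 14.0 list only progression or death.

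The analysis change costs SAP wording only and uses the same samples. Its downside is a smaller set and wider intervals: about 21–28 of 39 patients at C7D1, or 11–21 with 2–6 undetectable at C13D1, under the same assumptions.

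Separately, and not part of this fix, the MRD times in Section 2.3.1 (3 months; POD) should be reconciled with Section 3.1 (C3D1, after two cycles; end of treatment) and with Table 11-1. The research-blood row of that table cannot be read reliably in the text available here.

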15.0 TOXICITIES/RISKS/SIDE EFFECTS

An AE is defined as the appearance of (or worsening of any pre-existing) undesirable sign(s), symptom(s), or medical condition(s) that occur after patient's signed Informed Consent form has been obtained. Abnormal laboratory values or test results occurring after informed consent constitute AEs only if they induce clinical signs or symptoms, are considered clinically significant, require treatment (eg, hematologic abnormality that requires transfusion or hematologic stem cell support), or require changes in study medication(s).

AEs that begin or worsen after informed consent should be recorded in Medidata. Conditions that were already present at the time of informed consent should be recorded in the Medical History in Medidata. AE monitoring should be continued for at least 30 days following the last dose of study treatment or until initiation of new therapy, whichever comes first. AEs (including lab abnormalities that constitute AEs) should be described using a diagnosis whenever possible, rather than individual underlying signs and symptoms. When a clear diagnosis cannot be identified, each sign or symptom should be reported as a separate AE.

CTCAE Version 5 will be utilized for toxicity evaluation. If CTCAE grading does not exist for an AE, the severity of mild, moderate, severe, and life-threatening, corresponding to grades 1-4, will be used. CTCAE grade 5 (death) will not be used - rather, information about deaths will be collected through a Death form.

The occurring of AEs should be sought by non-directive questioning of the patient during the screening process after signing Informed Consent form and at each visit during the study. AEs also may be detected when they are volunteered by the patient during the screening process or between visits, or through physical examination, laboratory test, or other assessments. As far as possible, each AE should be evaluated to determine:

- The severity grade (CTCAE grade 1-4)
- Its duration (start and end dates)
- Its relationship to the study treatment (reasonable possibility that AE is related: yes or no)
- Action taken with respect to study or investigational treatment (none, dose adjusted, temporarily interrupted, permanently discontinued, unknown, or not applicable)
- Whether medication or therapy taken (no concomitant medication/non-drug therapy or concomitant medication/non-drug therapy)

- Outcome (not recovered/not resolved, recovered/resolved, recovering/resolving, recovered/resolved with sequelae, fatal, or unknown)
- Whether it is serious, as defined below
- All AEs should be treated appropriately. If a concomitant medication or non-drug therapy is given, this action should be recorded in Medidata.
- Once an AE is detected, it should be followed until its resolution or until it is judged to be permanent, and assessment should be made at each visit (or more frequently, if necessary) of any changes in severity, the suspected relationship to the study treatment, the interventions required to treat it, and the outcome
- Progression of malignancy (including fatal outcomes), if documented by use of appropriate method (Lugano criteria), should not be reported as an SAE
- AEs separate from POD (eg, deep vein thrombosis at time of progression or hemoptysis concurrent with finding of POD) will be reported as per usual guideline for such events with proper attribution regarding relatedness to the drug

Adverse events of special interest (AESIs) are a subset of events of scientific and medical concern specific to this study. Such an event may require further investigation in order to characterize and understand it. Depending on the nature of the event, rapid communication by the trial Sponsor to other parties (eg, regulatory authorities) may also be warranted. AESIs include IRRs, overdoses (defined as exceeding the planned dose by more than 20%), second primary malignancies, TFR, thromboembolic events, and TLS.

The 5 most common adverse events associated with tafasitamab/lenalidomide in the L-MIND study were neutropenia (51%), fatigue (38%), anemia (36%), diarrhea (36%), and thrombocytopenia (31%). Details on adverse events are described in Table 15-1.

Table 15-1: Adverse reactions in patients with relapsed or refractory diffuse large B-cell lymphoma who received tafasitamab in L-MIND (n = 81)

Adverse reactions occurring in	10%	All-grade%	Grade 3-4 %
Dermatologic			
Pruritus	10		1.2
Rash	15		2.5
Gastrointestinal			
Abdominal pain	15		1.2
Constipation	17		0
Decreased appetite	22		0
Diarrhea	36		1.2
Nausea	15		0
Vomiting	15		0
Hematologic			
Anemia	36		7
Febrile neutropenia	12		12

Neutropenia	51	49
Thrombocytopenia	31	17
Musculoskeletal		
Back pain	19	2.5
Muscle spasms	15	0
Other		
Fatigue	38	3.7
Hypokalemia	19	6
Peripheral edema	24	0
Pyrexia	24	1.2
Respiratory		
Bronchitis	16	1.2
Cough	26	1.2
Dyspnea	12	1.2
Respiratory tract infection	24	4.9
Urologic		
Urinary tract infection	17	4.9

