2.2 Secondary objectives

- 2.2.1** To determine disease control rate (DCR), defined as the percent of patients (relative to the total number evaluable) who achieve CR, PR, or stable disease (SD) at the time of ORR assessment.
- 2.2.2** To estimate DOR, defined as the time from achievement of PR or CR to progression of disease (POD) according to Lugano criteria.^{1,2}
- 2.2.3** To estimate PFS, defined as the time from initiation of study treatment to the earlier of POD or death from any cause.
- 2.2.4** To estimate OS, defined as the time from initiation of study treatment to death from any cause.
- 2.2.5** To estimate TTP, defined as the time from initiation of study treatment to POD or death from MCL.
- 2.2.6** To describe the safety of the combination of tafasitamab and lenalidomide in patients with R/R MCL, defined as the incidence and severity (according to National Cancer Institute Common Terminology Criteria for Adverse Events (CTCAE) version 5.0).

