10.5.4 Hematologic and other toxicities

Toxicities suspected to be related to study medications will be graded according to CTCAE version 5.0 and managed according to Tables 10-4 and 10-5 below.

Table 10-4: Hematologic and other toxicities suspected to be related to either study medication

Thrombocytopenia grade 3-4	Platelets < 50,000 cells/mcL	Cycles 1 through 3: interrupt both tafasitamab and lenalidomide Cycle 4: interrupt lenalidomide only Obtain CBC every 7 days
	Platelets recover to 50,000 cells/mcL	Provided other criteria for dosing are met (see 10.5.1), resume study treatment. If lenalidomide is being continued, it should be resumed at the next lower dose level. Dose re-escalation is permitted in certain circumstances (Table 10-6).

Neutropenia grade 3-4	ANC < 1,000 (but 500) cells/mcl for 7 days Or ANC < 1,000 cells/mcl with fever 38.5°C (101°F) Or ANC < 500 cells/mcl	Cycles 1 through 3: interrupt both tafasitamab and lenalidomide Cycle 4: interrupt lenalidomide only Obtain CBC every 7 days GCSF use is strongly encouraged
	ANC recovers to 1,000 cells/mcl	Provided other criteria for dosing are met (see 10.5.1), resume lenalidomide. If lenalidomide is being continued, it should be resumed at the next lower dose level. Dose re-escalation is permitted in certain circumstances (Table 10-6).
Other clinically significant toxicities (except those attributable to lenalidomide below)	Grade 3-4	Interrupt the study drug(s) to which the toxicity is suspected to be attributable.
	Resolution to grade :s; 2	Provided other criteria for dosing are met (see 10.5.1), resume previous treatment. If lenalidomide was interrupted and is being continued, it should be resumed at the next lower dose level (Table 10-6)

Table 10-5: Other toxicities suspected to be related to lenalidomide

Thromboembolic events	Grade 3-4	Interrupt lenalidomide dosing Start anticoagulation as per MSK anticoagulation guideline and investigator's discretion
	Resolution to grade :s; 2	Resume lenalidomide at investigator's discretion (maintain dose level)

Allergic reaction or hypersensitivity grade 3-4 (including but not limited to Stevens-Johnson syndrome, toxic epidermal necrolysis, exfoliative or bullous rash, angioedema)	Discontinue lenalidomide permanently
Desquamating (blistering) rash grade 3-4	Discontinue lenalidomide permanently

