11.0 EVALUATION DURING TREATMENT/INTERVENTION

11.1 General overview of evaluations

Evaluations during screening and study treatment are as indicated in Table 11-1.

Table 11-1. Schedule of evaluations (screening through cycle 3).

Day	Screening		Cycle 1 (28 days)					Cycle 2 (28 days)					Cycle 3 (28 days)				
	S 28 days before C1D1	S 7 days before C1D1	1	4	8	15	22	1	8	15	22	1	8	15	22	1	8
Window					±1	±1	±1	±1	±1	±1	±1	±1	±1	±1	±1	±1	±1
Informed consent	X																
Inclusion/exclusion checklist	X			X6													
Biopsy and pathologic confirmation of MCL	X																
PET	X															X	
CT CAP (+neck if indicated)	X															X	
KPS	X		X					X				X				X	
Vital signs ¹	X		X	X	X	X	X	X	X	X	X	X	X	X	X	X	X
Height			X														
Weight			X					X				X			X		
CBC with differential		X	X		X	X	X	X	X	X	X	X	X	X	X	X	X
Chemistry ²		X	X					X				X			X		
Hepatitis B serology	X																
Hepatitis C serology	X																
HIV serology	X																
Pregnancy test (if applicable) ³	X		X					X				X			X		
Consent to 12-245 IMPACT and sample collection ⁴	X																
BM aspirate and biopsy	X																
Research blood tests			X					X	X								
Optional research biopsy ⁵	X							X									
(S)AE assessment	X	X	X	X	X	X	X	X	X	X	X	X	X	X	X	X	X
Tafasitamab administration			X	X	X	X	X	X	X	X	X	X	X	X	X	X	X
Lenalidomide administration																	
Patients will self-administer Days 1-21 of each Cycle																	

Table 11-1 (continued). Schedule of evaluations (cycles 4 through EOT).

	Cycle 4 (28 days)	Cycle 5 (28 days)	Cycle 6 (28 days)	Cycle 7 (28 days)	Cycle 8 (28 days)	Cycle 9 (28 days)	Cycle 10 (28 days)	Cycle 11 (28 days)	Cycle 12 (28 days)	Cycle 13 (28 days)	Cycles 14-36 (28 days each)	EOT visit
Day	1	15	1	15	1	15	1	15	1	15	1	1
PET Scan												
CT CAP												
Biopsy												
KPS	X	X	X	X	X	X	X	X	X	X	X ⁸	X ⁹
Vital signs ¹	X	X	X	X	X	X	X	X	X	X	X	X ⁹
Weight	X	X	X	X	X	X	X	X	X	X	X	X ¹⁰
CBC with differential	X	X	X	X	X	X	X	X	X	X	X	X
Chemistry ²	X	X	X	X	X	X	X	X	X	X	X	
Pregnancy test (if applicable) ³	X	X	X	X	X	X	X	X	X	X	X	
BM aspirate and biopsy												
Research blood tests	X											
Optional research biopsy ⁵												
(S)AE assessment	X	X	X	X	X	X	X	X	X	X	X	X
Tafasitamab administration	X	X	X	X	X	X	X	X	X	X	X	X
Lenalidomide administration												

Patients will self-administer Days 1-21 of each Cycle

¹Vitals: Blood Pressure, Pulse, Respiratory Rate, and Temperature

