14.0 BIOSTATISTICS

Objectives:

The primary objective is to estimate the ORR, defined as the percent of patients (relative to the total number considered evaluable as in 13.2) who achieve CR or PR. The primary endpoint will be analysed when all patients have completed 12 cycles of treatment or at treatment discontinuation, whichever comes first.

Secondary objectives are estimates of OCR, DOR, PFS, OS, and TTP, and descriptions of incidence and severity of AEs. Exploratory objectives include rate of conversion to undetectable MRD, ctDNA/clonal evolution, antitumor immune response, and effects on tumor microenvironment immunosuppression.

Exploratory objectives are described in Section 3.1 Correlative studies.

Study design:

The primary endpoint is ORR and the study is designed to determine preliminary clinical effectiveness of tafasitamab and lenalidomide. Based upon limited data available for lenalidomide and associated combinations in the post-BTKi setting, the combination of tafasitamab and lenalidomide will be considered worthy of further evaluation if the ORR is greater than 30%. This combination will be considered promising in the R/R setting if the ORR is greater than 50% given multiple evolving treatment options for patients post-BTKi failure or intolerance. To this end, , a single-arm Simon's two-stage minimax design will

utilize a null (non-promising) ORR of 30% and an alternative (promising) ORR of 50%. In the first stage, a total of 19 patients will accrue. If 6 or fewer have objective response, the trial will close due to a lack of efficacy; otherwise, an additional 20 patients will accrue. If at the end of the study, 17 or more out of 39 have an objective response, the trial will be considered promising for future development. This design will give 80% power with a type I error rate of 5%. Patients will continue to enroll without holding enrollment while the interim analysis is evaluated in the first 19 patients.

The anticipated accrual rate for this study is 1 to 2 patients per month. We anticipate total accrual will be completed in 2-3 years. The study will continue enrollment until the required number of evaluable patients (those that receive at least one dose of both study drugs) is reached in each stage of the study.

Methods:

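### Safety is summarised only through recorded AEs, so some cytopenias seen in scheduled blood counts, mainly lower-grade ones, may never be reported

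*Combined protocol and SAP*

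**What the plan says.** Objective 2.2.6 is "To describe the safety of the combination of tafasitamab and lenalidomide in patients with R/R MCL", measured as incidence and severity under CTCAE v5.0. Section 14.0 restates this as "descriptions of incidence and severity of AEs", and its Methods give one analysis: "Frequency and severity of adverse events will be summarized descriptively". The safety population is everyone dosed with either drug.

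Section 15.0 decides which laboratory findings enter that summary. Abnormal values "constitute AEs only if they induce clinical signs or symptoms, are considered clinically significant, require treatment", and the sentence then adds a fourth route, "or require changes in study medication(s"). The second route, clinical significance, is a judgement with no stated criterion.

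Table 11-1 schedules "CBC with differential" at nearly every treatment visit. No section describes a summary of worst laboratory grade or of shift from baseline.

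**The concern.** The trial measures blood counts on a fixed schedule, but its planned report shows only those abnormalities that pass the Section 15.0 filter. One of the four routes through the filter is the view of an open-label investigator. The filter can remove events but cannot add them, so recorded cytopenia incidence can only be equal to or below the incidence found by grading the same measurements.

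Haematologic toxicity is the main toxicity expected. Section 15.0 reports all-grade rates from the earlier DLBCL study of 51% for neutropenia, 36% for anaemia and 31% for thrombocytopenia. With no control arm, readers will set this trial's rates against those of other studies, and Section 3.0 hopes for an effective regimen with little toxicity. A rate that depends partly on judgement and attribution is a weak basis for that comparison.

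**Working it through.** The plan states no figure on this point, so there is none to reproduce. The check sets the recording rule against the rules that force a drug change.

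**What the drug-change route captures**

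- Table 10-4 requires interruption for platelets below 50,000, ANC below 500, ANC below 1,000 with fever, and ANC 500 to under 1,000 persisting for 7 days. Both drugs stop in cycles 1-3. For later cycles the table reads "Cycle 4: interrupt lenalidomide only". Lenalidomide, if continued, resumes one level lower.
- Section 10.5.1 sets ANC 1,000 and platelets 50,000 as conditions for starting each cycle, unless the low count is put down to MCL. I read a held cycle as a change in study medication.
- While lenalidomide is being given, most grade 3-4 thrombocytopenia and neutropenia therefore becomes an AE under the protocol's own definition.

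**What can still escape, if symptom-free, untreated and not judged significant**

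| Finding | Why no drug change is forced |
|---|---|
| Grade 1-2 neutropenia or thrombocytopenia | Above the Table 10-4 and 10.5.1 limits |
| Anaemia | No row of its own in Table 10-4 and no day 1 limit in 10.5.1; capture rests on transfusion or other treatment, or on the catch-all row, which again turns on clinical significance |
| Afebrile ANC 500 to under 1,000 for less than 7 days, outside day 1 | Does not meet the Table 10-4 duration condition |
| Low counts attributed to MCL | Exempt from the day 1 condition; Table 10-4 covers only toxicity suspected to be drug-related |
| Cytopenia on tafasitamab alone from cycle 4, between day 1 checks | Table 10-4 then interrupts only lenalidomide, which has already stopped |

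The MCL row is foreseeable: Section 6.1 waives the ANC and platelet limits for low counts put down to MCL, and Section 3.0 names bone marrow as a common site of disease.

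**Illustration of where the loss would fall**

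Inputs are the Table 15-1 rates and the planned 39 evaluable patients (the safety population may be slightly larger). Assume that those rates apply, that every grade 3-4 event is recorded, and that between none and all of the lower-grade events are recorded. The largest shortfall is then 39 × (all-grade rate − grade 3-4 rate).

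- Neutropenia: 39 × (0.51 − 0.49) = 19.9 − 19.1 = 0.8 patients; reported rate 49% to 51%.
- Thrombocytopenia: 39 × (0.31 − 0.17) = 12.1 − 6.6 = 5.5 patients; reported rate 17% to 31%.
- Anaemia: 39 × (0.36 − 0.07) = 14.0 − 2.7 = 11.3 patients; reported rate 7% to 36%.

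These are not estimates. Table 15-1 is itself a table of adverse reactions whose recording rule is not given, so its rates may already be filtered. The assumption of full grade 3-4 capture is also generous for anaemia and for brief grade 3 neutropenia.

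**The case against.** The strongest reply is that the serious events are already caught. Drug changes under Table 10-4, the day 1 condition, and treatment with G-CSF (strongly encouraged in the neutropenia row) or transfusion all make a value an AE. Incidence is also counted per patient, so one qualifying episode is enough, and the brief grade 3 gap matters only for patients who never have one. This stands, and it confines the concern to the categories tabulated above.

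A reader might infer that Section 15.0 contradicts the endpoint. It does not: Section 14.0 speaks of AEs and Section 15.0 defines them. What is missing is a supplementary summary.

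A reader might also take the 49% grade 3-4 neutropenia in Table 15-1 as a true laboratory rate and multiply it by an assumed capture share. The documents give no capture share, and the 49% is an adverse-reaction rate, so this could filter the same events twice. A low share would also conflict with Table 10-4.

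Finally, scheduled counts do not reveal every patient's true worst grade. Treatment visits become two-weekly from cycle 4 and four-weekly in maintenance, so nadirs between visits are missed. Laboratory grades also include disease-related cytopenia. Both facts argue for placing a laboratory table beside the AE table, not in its place.

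**Conclusion.** The concern holds in a limited form. Followed as written, the plan yields cytopenia rates that depend partly on undefined judgement and attribution, and that can only be equal to or below the CTCAE-graded rates from the same measurements. The loss falls mainly on grade 1-2 events and the other categories listed, and only partly on grade 3-4 neutropenia or thrombocytopenia during lenalidomide. The documents do not support a claim of large under-reporting of those grade 3-4 events, and they do not allow any figure for the total.

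This conclusion assumes that a held cycle counts as a drug change and that the investigator applies Section 15.0 as worded. An investigator who calls every abnormal count significant would leave little gap. Safety is a descriptive secondary objective with no decision rule attached in Section 14.0, so this is an inexpensive improvement worth making and not an error in the design.

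**What to change.** Add to Section 14.0, Methods, under secondary objectives:

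> Scheduled haematology and chemistry values will be graded by CTCAE v5.0 from the laboratory results where a numeric grade exists. Worst post-baseline grade and shift from baseline will be tabulated in the safety population alongside the AE table, labelled as laboratory abnormalities.

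The cost is one or two extra tables from measurements already scheduled. The sponsor should confirm that all scheduled values reach the study database, since Section 16.2 does not say so explicitly.

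The drawbacks should be stated with the table. Laboratory rates will look higher than AE rates, will include disease-related cytopenia (hence the shift from baseline), and will miss nadirs between visits. They should not replace the AE rates or be compared directly with Table 15-1. Treatment rules, sample size, type I error, power and the response rule do not change.
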